8.2. Adverse Event Definitions

Adverse Event (AE): any untoward medical occurrence, unintended disease or injury, or untoward clinical signs (including abnormal laboratory findings) in subjects, users, or other persons, whether or not related to the investigational medical device and whether anticipated or unanticipated. This includes events related to the investigational device or the comparator and to the procedures involved. For users or other persons, this is restricted to events related to the use of investigational medical devices or comparators.

Serious Adverse Event (SAE): an adverse event that led to death; led to a serious deterioration in the health of the subject, users, or other persons as defined by one or more of the following: a life-threatening illness or injury, a permanent impairment of a body structure or a body function including chronic disease, or in-patient or prolonged hospitalization, or medical or surgical intervention to prevent life-threatening illness or injury or permanent impairment to body structure or a body function; or led to fetal distress, fetal death or a congenital abnormality or birth defect including physical or mental impairment. Planned hospitalization for a pre-existing condition, or a procedure required by the protocol without serious deterioration in health, is not considered a SAE.

Adverse Device Effect (ADE): an adverse event related to the use of an investigational or comparator medical device. This includes any adverse events resulting from insufficient or inadequate instructions for use, deployment, implantation, installation, or operation, or any malfunction of the investigational medical device. This includes any event that is a result of a user error or intentional misuse of the investigational device.

Study Title: Maternal Fetal Device Performance Testing During Antepartum Singleton Monitoring

Study Number: SA-000072

Version Number: 2.0

Version Date: 23SEP2024

GE HealthCare

Serious Adverse Device Effect (SADE): an adverse device effect that has resulted in any of the consequences characteristic of a serious adverse event.

Unanticipated serious adverse device effect (USADE): a serious adverse device effect, which by its nature, incidence, severity, or outcome has not been identified in the current risk assessment.

Serious health threat: signal from any AE or device deficiency that indicates an imminent risk of death or a serious deterioration in the health of subjects, users, or other persons, and that requires prompt remedial action for other subjects, users, or other persons.

8.3. Documentation of Adverse Events

All adverse events (AE), including all serious adverse events (SAE), are required to be collected, investigated, and documented. AEs will be collected from subject enrollment period, and during scanning period for each visit. All AEs will be followed through to their resolution. Documentation will include:

- Description of Event
- Date of onset
- Date of resolution unless resolution does not occur during study reporting period. In the instance that resolution does not occur, the status of the AE will be documented (not resolved/recovered or resolving/recovering)
- Severity (mild, moderate, or severe)
 - *Mild:* Symptom(s) barely noticeable to the subject or does not make the subject uncomfortable. The AE does not influence performance or functioning. Prescription drugs are not ordinarily needed for relief of symptom(s).
 - *Moderate:* Symptom(s) of a sufficient severity to make the subject uncomfortable. Performance of daily activities is influenced. Treatment of symptom(s) may be needed.
 - *Severe:* Symptom(s) of a sufficient severity to cause the subject severe discomfort. Treatment for symptom(s) may be given.
- Serious (yes/no)
- Causal relationship to investigational or comparator medical device? (not related, possible, probable, or causal relationship)
 - *Not related:* Relationship to the device, comparator or procedures can be excluded when:
 - the event has no temporal relationship with the use of the investigational device, or the procedures related to application of the investigational device;
 - the serious adverse event does not follow a known response pattern to the medical device (if the response pattern is previously known) and is biologically implausible;
 - the discontinuation of medical device application or the reduction of the level of activation/exposure - when clinically feasible - and reintroduction of its use (or increase of the level of activation/exposure), do not impact on the serious adverse event;
 - the event involves a body-site or an organ that cannot be affected by the device or procedure;
 - the serious adverse event can be attributed to another cause (e.g., an underlying or concurrent illness/clinical condition, an effect of another device, drug, treatment or other risk factors);
 - the event does not depend on a false result given by the investigational device used for diagnosis, when applicable;

Study Title: Maternal Fetal Device Performance Testing During Antepartum Singleton Monitoring

Study Number: SA-000072

Version Number: 2.0

Version Date: 23SEP2024

GE HealthCare

In order to establish the non-relatedness, not all the criteria listed above might be met at the same time, depending on the type of device/procedures and the serious adverse event.

- *Possible*: The relationship with the use of the investigational device or comparator, or the relationship with procedures, is weak but cannot be ruled out completely. Alternative causes are also possible (e.g., an underlying or concurrent illness/ clinical condition or/and an effect of another device, drug or treatment). Cases where relatedness cannot be assessed, or no information has been obtained should also be classified as possible.
- *Probable*: The relationship with the use of the investigational device or comparator, or the relationship with procedures, seems relevant and/or the event cannot be reasonably explained by another cause.
- *Causal relationship*: the serious adverse event is associated with the investigational device, comparator or with procedures beyond reasonable doubt when:
 - the event is a known side effect of the product category the device belongs to or of similar devices and procedures;
 - the event has a temporal relationship with investigational device use/application or procedures;
 - the event involves a body-site or organ that:
 - the investigational device or procedures are applied to;
 - the investigational device or procedures have an effect on;
 - the serious adverse event follows a known response pattern to the medical device (if the response pattern is previously known);
 - the discontinuation of medical device application (or reduction of the level of activation/exposure) and reintroduction of its use (or increase of the level of activation/exposure), impact on the serious adverse event (when clinically feasible);
 - other possible causes (e.g., an underlying or concurrent illness/clinical condition or/and an effect of another device, drug or treatment) have been adequately ruled out;
 - harm to the subject is due to error in use;
 - the event depends on a false result given by the investigational device used for diagnosis, when applicable;

In order to establish the relatedness, not all the criteria listed above might be met at the same time, depending on the type of device/procedures and the serious adverse event.

- Causal relationship to investigational procedure (not related, possibly related, probably related, or causal relationship)
- Treatment given and/or action taken (procedure stopped, withdrawn from study, or no action)
- Anticipated (yes/no)
- Signals from AE that might indicate a serious health threat.

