4.2. Study Population

Subjects meeting all inclusion criteria will be consented for enrollment in the study. Subjects enrolled are expected to be representative of the general population prescribed to receive electronic fetal monitoring.

- Singleton pregnancy
- Greater than or equal to 22 0/7 weeks gestation
- Aged 18+

Participation is expected to last approximately 90 minutes.

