5. STUDY PROCEDURES

5.1. Subject Preparation

Study staff will confirm that the subject is eligible and complies with applicable site requirements prior to starting study procedures.

After providing consent, the subject will be enrolled in the study.

Pregnant women of \geq 22 weeks gestation will undergo two 30 (+5 minute range) -minute monitoring sessions (60 minutes total).

Study Title: Maternal Fetal Device Performance Testing During Antepartum Singleton Monitoring

Study Number: SA-000072

Version Number: 2.0

Version Date: 23SEP2024

GE HealthCare

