10.3.3. Safety Analysis

a. Analysis of Adverse Events

Study Title: Maternal Fetal Device Performance Testing During Antepartum Singleton Monitoring

Study Number: SA-000072

Version Number: 2.0

Version Date: 23SEP2024

GE HealthCare

When applicable, AE will be listed per subject, summarized with counts and percentages of events, and summarized with counts and percentages of subjects with events.

When applicable, the incidence of AE will be computed by the number of AEs divided by the total enrolled subjects. The AEs will be categorized into different groups and reported using summary tables and listings.

b. Analysis of Device Deficiencies/Complaints

If applicable, the device deficiencies will be reported using summary tables and listings. The incidence of device deficiencies will be computed by the number of device deficiencies divided by their corresponding totals.

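### Section 8.3 pools the investigational and comparator monitors in one causality item and asks only for the onset date, so the required AE fields do not show which monitor is implicated

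*Combined protocol and SAP*

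**What the plan says.** **AE fields (Section 8.3).** The listed documentation includes a free-text entry ("Description of Event"), dates of onset and resolution, severity, seriousness, action taken, and whether the event was anticipated. Device causality is a single question with one four-level answer: "Causal relationship to investigational or comparator medical device? (not related, possible, probable, or causal relationship"). A second question covers the procedure: "Causal relationship to investigational procedure (not related, possibly related, probably related, or causal relationship"). No onset time, session or device in use is listed.

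**Category definitions (Section 8.3).** *Possible* is defined over both devices and the procedures together: "The relationship with the use of the investigational device or comparator, or the relationship with procedures, is weak but cannot be ruled out completely". *Probable* pools them in the same way. One listed ground for *not related* is that "the event has no temporal relationship with the use of the investigational device, or the procedures related to application of the investigational device". The matching timing criterion under *causal relationship* also names the investigational device and procedures, not the comparator.

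**Exposure.** Section 4.8 requires 30 minutes of monitoring on each device for a subject to count as complete. Section 5.1 sets two 30 (+5) "minute monitoring sessions (60 minutes total"). Section 4.2 states: "Participation is expected to last approximately 90 minutes".

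**Analysis (Section 10.3.3).** When applicable, "AE will be listed per subject, summarized with counts and percentages of events" and of subjects with events. Incidence is the number of AEs over all enrolled subjects. AEs are also to be put into groups, which are not named. No table by device is specified.

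**The concern.** In a parallel-group study a pooled causality item does little harm, because the arm shows which device the subject had. Here each completed subject has both, so the subject identifier carries no information about the device. The attribution has to come from the AE record itself, and the required structured fields do not ask for it.

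The study compares a new monitor with a cleared one (Section 3.1), its safety endpoint is the type and number of AEs, SAEs and device issues (Section 3.2.3), and the results are meant for FDA 510(k) and CE submissions (Section 1). The anticipated events in Section 8.1, mainly skin reactions and discomfort from transducer, belt or gel, could arise with either monitor. An AE list that does not separate the new monitor from its comparator is a weaker safety statement than the design could give. The device in use is also easiest to record at the time, since no follow-up is planned after participation other than following AEs to resolution (Section 5.3).

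**Working it through.** No plan figure needs reproducing and no power or margin is involved. The check is whether the required fields, taken together, identify the device for an AE that starts during the visit.

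1. **Can the onset date separate the exposures?** Session time is 2 × 30 = 60 minutes, or 2 × 35 = 70 minutes with the allowed range. Both fit within the visit of about 90 minutes. The two sessions therefore share a date. The date can separate two visits by a woman who enters more than one gestational age group (allowed by the note in Section 4.5.2), but not two sessions in one visit.

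2. **Can the causality answer separate them?** The item has four levels. *Not related*, properly reached, clears both devices. Each of the other three is compatible with the investigational device only, the comparator only, or both. Three of the four levels leave the device open.

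3. **Does another required field help?** The procedure item separates procedure from device to some extent, but is not split by device. Section 6.3 adds device relatedness without saying which device. The definition of an adverse device effect in Section 8.2 also covers both devices. The free-text description may name the device, but is not required to.

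4. **Do the criteria fit the item?** The question covers the comparator, and the lead-in to *not related* mentions it, but the timing criteria under *not related* and *causal relationship* refer to the investigational device. Suppose a reaction arises and ends in a session where the comparator was used first. It has no temporal link to the investigational device, so it meets one listed ground for *not related* on a question that also asks about the comparator. The timing criteria also rely on information finer than the date that is recorded.

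5. **Does the analysis recover it?** Section 10.3.3 lists AEs per subject and divides by total enrolled. With both devices used in each completed subject, neither step yields a result by device.

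For an in-visit AE rated possible, probable or causal in a subject who used both devices, the required structured fields do not identify the device.

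**The case against.** The strongest reply is that the protocol is not the whole record. Section 8.3 requires AEs to be investigated, its field list is not stated to be exhaustive, and neither the eCRF nor its completion guidelines are among the documents. The procedure steps are redacted, so what staff note at the start, changeover or end of a session is unknown. This stands: a device-specific field elsewhere can be neither confirmed nor excluded. What can be said is that the protocol does not require one.

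Four stronger readings are tempting and are not supported.

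- *No AE can be attributed to a device.* The description or the investigation may settle single cases, a *not related* rating needs no split, and a subject who stopped before the second session used only one device.
- *Device effects cannot be told from gel and belt effects.* A separate procedure item exists. The separation is imperfect, because the device-causality definitions also mention procedures, but it is not absent.
- *The criteria force comparator events into not related.* They do not. *Possible* and *probable* expressly include the comparator, cases that cannot be assessed go to *possible*, and no single criterion is said to be decisive. The wording is loose and uneven.
- *Device deficiencies have the same gap.* They are reported under Section 8.5 and analysed separately in Section 10.3.3; the AE causality item does not govern them.

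It is also fair to say that the safety endpoint is descriptive, with no comparative safety hypothesis, that the expected risks are described as minimal, and that Section 10.3.3 permits grouping by device without requiring it.

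**Conclusion.** The point holds as a limited gap. The required structured fields do not separate the investigational monitor from the comparator for an in-visit AE rated possible, probable or causal, and no by-device summary is planned. The uneven timing criteria add ambiguity.

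The size is small: a minor improvement, with no bearing on the primary analysis of FHR success rate. The documents give no expected AE rate, so the number of affected events is not estimated. Confidence is moderate. The conclusion assumes that both sessions take place in one visit, as the stated durations imply, and that the unseen eCRF adds no device-specific field. If it already has these fields, the protocol need only state them and the by-device table.

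**What to change.** In Section 8.3:

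- Split the device-causality item into one for the investigational device and one for the comparator.
- Keep the existing procedure item and state that it covers the shared gel, belt and positioning.
- Record the clock time of onset with the date, and the session and device in use at onset (first session, changeover, second session, after removal).
- Reword the timing criteria so that they refer to the device being assessed.

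In Section 10.3.3, tabulate AEs by device in use at onset and by device-specific relatedness.

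The cost is a few extra eCRF fields and one table, with no added visits or subjects. The remedy is partial: a reaction that appears in the second session may still be rated *possible* for both devices because of carry-over from the first. The device in use at onset should therefore be read alongside the causality ratings and not in place of them.

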8.4. Reporting of Safety Events

The following events are to be reported to the Sponsor within 72 hours of the event occurrence and to the EC per their policy:

- All SAEs and USADEs

Study Title: Maternal Fetal Device Performance Testing During Antepartum Singleton Monitoring

Study Number: SA-000072

Version Number: 2.0

Version Date: 23SEP2024

GE HealthCare

- All device issues that could possibly lead to an SAE
- Any signal from an AE that might indicate a serious health threat
- Unanticipated AE and unanticipated ADEs

Additional follow-up information may be requested by the Sponsor. In addition, safety information may be shared with regulatory agencies and other participating sites, as required by applicable law and regulation.

The Sponsor contact for reporting safety events:

[REDACTED]
[REDACTED]

8.5. Reporting of Device Deficiencies/Complaints

Device deficiency: an inadequacy of a medical device with respect to its identity, quality, durability, reliability, usability, safety, or performance, such as malfunctions, use errors, and inadequacy in the information supplied by the manufacturer including labelling.

Device deficiencies/complaints should be reported to the study Sponsor contact identified on the cover page of this protocol. All device deficiencies/complaints will be collected, fully investigated, and documented in the source document during the study reporting period. The Principal Investigator is responsible for notifying the Sponsor in the event that there is any device issue that could potentially lead to a SAE.

9. ETHICAL CONDUCT OF THE STUDY

The study will be carried out per the protocol and with principles enunciated in the current version of the Declaration of Helsinki; the guidelines of Good Clinical Practice (GCP) for medical devices, as set forth by ISO 14155 and ISO 14971; applicable sections of United States FDA 21 Code of Federal Regulations (CFR); and applicable regulatory authority's requirements of the site.

The study will be conducted and reported per applicable policies of the Ethics Committee (EC) and governing regulatory authorities.

If national or regional EC requirements are less strict than the requirements of GCP, such as ISO 14155 for medical devices, the Sponsor shall apply the requirements of this International Standard to the greatest extent possible, irrespective of any lesser requirements, and shall record such efforts.

9.1. Ethics Committee

The responsible Principal Investigator at each site will ensure that approval from an appropriately constituted EC is attained for the clinical study prior to enrolling subjects, and the Principal Investigator will ensure that documentation of approval is maintained for the duration of the study.

The Principal Investigator will ensure that the Sponsor is notified of any withdrawal of EC approval within 5 working days of such occurrence. If approval is terminated or suspended, the Principal Investigator will notify the Sponsor and provide written explanation.

Study Title: Maternal Fetal Device Performance Testing During Antepartum Singleton Monitoring

Study Number: SA-000072

Version Number: 2.0

Version Date: 23SEP2024

GE HealthCare

9.2. Regulatory Agencies and Competent Authority(ies)

The Sponsor will obtain approval from the local regulatory agency or competent authority before the start of the clinical study, if necessary, per applicable local laws and regulations. Any additional requirements imposed by the EC or regulatory authority shall be followed, if applicable.

9.3. Management of Protocol Modifications and Amendments

Substantial amendments will only be implemented after approval of the EC. Non-substantial modifications may be made during the normal course of device optimization, maintenance, and feasibility testing. Non-substantial modifications will be communicated to the competent authority (CA) as soon as possible, if applicable, and to the EC per their policy.

9.4. Management of Protocol Deviations

A deviation is any instance(s) of failure to follow, intentionally or unintentionally, the requirements of the protocol. Under emergency circumstances, deviations from the protocol to protect the rights, safety, and wellbeing of human subjects may proceed without prior approval of the Sponsor and the EC/CA. Such deviations shall be documented and reported to the Sponsor and the EC/CA as soon as possible. Deviations will be reported as:

- **Critical Deviations:** Deviations that significantly affect the safety, efficacy, integrity, or conduct of the study. These deviations must be reported to the Sponsor no later than 5 working days from awareness of occurrence and reported to the EC per the deviation reporting policy.
- **Non-Critical Deviations:** Protocol deviations that do not significantly affect the safety, efficacy, integrity, or conduct of the study. These deviations must be documented on the CRF Protocol Deviation page and will be reviewed by the study monitor.

The Sponsor will assess and implement any corrective or preventative actions necessary, such as retraining the study staff and PI.

9.5. Subject Information and Informed Consent

The investigators will explain to each subject the nature of the study, its purpose, the procedures involved, the expected duration of exposure to the investigational device (if applicable), the potential risks and benefits, and any potential discomforts. Each subject will be informed that participation in the study is voluntary, that she may withdraw from the study at any time, and that withdrawal of consent will not affect her subsequent medical assistance and treatment. The subject must be informed that her medical records may be examined by authorized individuals other than their treating physician.

All subjects for the study will be provided an informed consent form (ICF), describing the study and providing sufficient information to allow the subject (i) to make an informed decision about her participation in the study, and (ii) to be fully aware of her rights under the applicable law. Informed consent documents will be subject to approval by the EC prior to enrolling subjects in the study.

The subject should read and consider the statement before signing and dating the ICF and shall be given a copy of the signed document. The ICF must also be signed and dated by the investigator (or his/her designee), and it shall be retained as part of the study records.

Study Title: Maternal Fetal Device Performance Testing During Antepartum Singleton Monitoring

Study Number: SA-000072

Version Number: 2.0

Version Date: 23SEP2024

GE HealthCare

